5 STATISTICAL METHODS

In this Phase 2 dose-finding study of BAN2401 for the treatment of Early Alzheimer's Disease, response adaptive randomization will be used to allocate subjects to placebo control or 1 of the 5 active doses with the goal of characterizing the dose response. The study will be monitored for early success and early futility. The sponsor intends that the futility rule for stopping will be binding. If the study continues to randomize subjects after futility boundary has been crossed, it will be considered a failed study.

All statistical analyses for Core Study will be performed by the sponsor or designee. All of the Bayesian analysis will be conducted by an external IMC. The sponsor and investigators will be blinded to the IA data and outputs. The detailed processes and procedures related to study success at IA and the Bayesian analysis at 12 months are defined in a separate integrity charter. All other statistical analyses for Core Study will be performed by the sponsor or designee after the database is locked and released for unblinding. At each IA of the primary endpoint, a snapshot of the data will be obtained and released for analysis. A copy of this snapshot will be archived. This process will also be followed for the safety data that will be used for analysis for the DSMB. Statistical analyses will be performed using SAS software or other validated statistical software as required. All statistical tests for conventional analysis will be based on the two-sided 10% or one-sided 5% level of significance. The definition of success at primary analysis based on Bayesian methods is given in [Section 5.4.2 Adaptive Trial Definitions](#).

All descriptive statistics for continuous variables will be reported using mean, standard deviation (SD), median, minimum and maximum. Categorical variables will be summarized as number (percentage) of subjects.

5.1 STUDY ENDPOINTS

5.1.1 Primary Endpoint(s)

- Change from baseline in the derived ADCOMS at 12 months

5.1.2 Key Secondary Endpoint(s)

- Change from baseline at 18 months in brain amyloid pathophysiology as measured by amyloid PET
- Change from baseline in the derived ADCOMS at 18 months
- Change from baseline in CDR-SB at 18 months
- Change from baseline in ADAS-Cog at 18 months
- Change from baseline in CSF biomarkers (A β [1-42], t-tau, and p-tau) at 18 months
- Change from baseline in total hippocampal volume at 18 months using vMRI

5.1.3 Secondary Endpoint(s)

- Change from baseline at 12 months in brain amyloid pathophysiology as measured by amyloid PET
- Change from baseline at 12 months on clinical status for the following assessments: ADCOMS, CDR-SB, and ADAS-Cog

- Change from baseline in CSF biomarkers (A β [1-42], t-tau, and p-tau) at 12 months
- Change from baseline in total hippocampal volume at 6 and 12 months, and in left and right hippocampus, whole brain, and total ventricular volume as measured by vMRI at 6, 12, and 18 months

5.1.4 Exploratory Endpoint(s)

- Change from baseline in clinical status across all time points not analyzed in Key Secondary and Secondary sections for ADCOMS, CDR-SB, ADAS-Cog, MMSE, and FAQ

5.2 STUDY SUBJECTS

5.2.1 Definitions of Analysis Sets

The number (percent) of subjects included in each analysis set will be presented by analysis set, treatment group and overall. The description of the analysis data sets are:

The Randomized Set is the group of subjects who are randomized to study drug.

The Safety Analysis Set is the group of subjects who receive at least 1 dose of study drug and have at least 1 post dose safety assessment.

The Full Analysis Set is the group of randomized subjects who receive at least 1 dose of study drug and have baseline and at least 1 post dose primary efficacy measurement.

The PK Analysis Set is the group of subjects with at least 1 quantifiable BAN2401 serum concentration with a documented dosing history.

The PD Analysis Set is the group of subjects who have sufficient PD data to derive at least 1 PD parameter.

The Per Protocol (PP) Analysis Set is the subset of subjects in the Full Analysis Set who complied with the protocol.

5.2.2 Subject Disposition

The number of subjects screened, the number (percent) of subjects who failed screening, and the reasons for screen failure will be summarized, based on data reported on the Screening Disposition eCRF. The distribution of the number of randomized subjects by each site will be summarized for each randomized treatment group. The primary reasons for screen failures; did not meet inclusion or met exclusion criteria, AE, lost to follow-up, withdrawal consent, and other, will be presented.

Study Completion: the number (percent) of randomized and treated subjects who completed the study and who discontinued from the study will be summarized according to the primary

reason for discontinuation and secondary reason(s) for discontinuation, based on data reported on the Subject Disposition (Study Phase) CRF. The number (percent) will be presented by treatment group and total for subjects; randomized, not treated, treated, who completed the study, and discontinued from the study. The primary reasons for discontinuation from the study are; AE, lost to follow-up, subject choice, withdrawal of consent, pregnancy, study terminated by sponsor, and other. The secondary reasons for discontinuation from the study are: AE, subject choice, and other.

Completion of Study Treatment: the number (percent) of randomized and treated subjects who completed study treatment and who discontinued from study treatment will be summarized according to the primary reason for discontinuation and also according to secondary reason(s) for discontinuation, based on data reported on Early Discontinuation from Study Drug eCRF. The number (percent) will be presented by treatment group and total for subjects; randomized, not treated, treated, who completed study treatment, and discontinued from study treatment. The primary reasons for discontinuation from the study treatment are: AE, subject choice, inadequate therapeutic response, pregnancy, and other. The secondary reasons for discontinuation from the study are: AE, subject choice, inadequate therapeutic effect, and other. Subjects who discontinued study treatment but were followed up for efficacy assessments post treatment will also be summarized.

5.2.3 Protocol Deviations

A listing of subjects with protocol deviations will be provided by subject along with the description of the protocol deviation. Protocol deviations will be identified prior to database lock.

5.2.4 Demographic and Other Baseline Characteristics

Demographic and baseline characteristics for the Safety Analysis set and Full Analysis set will be summarized for each treatment group and baseline PET SUVR subgroup defined in [Section 5.8](#) using descriptive statistics. Continuous demographic and baseline variables include age, ADCOMS, ADAS-Cog, CDR-SB, FAQ, and MMSE; categorical variables include age < 65, age ≥ 65 to <80, age ≥ 80, sex, race, ethnicity, region, Global CDR score, memory box score of the CDR, *APOE ε4 carrier status* (positive (overall, heterozygous and homozygous) and negative), ongoing treatment with AChEIs and/or memantine (yes or no), and clinical subgroup (MCI due to AD and Mild Alzheimer's Disease Dementia).

The status of the disease at screening for each clinical subgroup (MCI due to AD and Mild Alzheimer's Disease Dementia) will be summarized according to the number of years the subject had the disease since diagnosis and onset of symptoms, his/her age at diagnosis, and age at onset of symptoms (summarized both as a continuous variable and as a categorical variable, with categories 30 to < 50 years, ≥ 50 to < 65 years, ≥ 65 years to < 80, and ≥ 80).

MEDICAL HISTORY

The medical history verbatim descriptions (investigator terms from the CRF) will be classified into standardized medical terminology using the Medical Dictionary for Regulatory Activities (MedDRA). Medical history will be coded to the MedDRA (Version 15.0 or higher) lower level term (LLT) closest to the verbatim term. The linked MedDRA preferred term (PT) and primary system organ class (SOC) will also be captured in the database.

The number (percent) of subjects will be presented by SOC and PT for each treatment group.

5.2.5 Prior and Concomitant Therapy

All investigator terms for medications recorded in the CRF will be coded to an 11-digit code using the World Health Organization Drug Dictionary (WHO DD). The number (percentage) of subjects who took prior and concomitant medications will be summarized on the Safety Analysis Set by treatment group, Anatomical Therapeutic Chemical (ATC), and WHO DD preferred term. Prior medications are defined as medications that stopped before the first dose of study drug. Concomitant medications are defined as medications that (1) started before the first dose of study drug and were continuing at the time of the first dose of study drug, or (2) started on or after the date of the first dose of study drug and continued up to the last dose. Prior and concomitant therapies for AD and those for non-AD will be summarized separately.

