The primary endpoint is the change from baseline to 12 months in the derived ADCOMS. The primary efficacy analysis is based on Bayesian statistics. The dose-response of the primary endpoint is modeled with a two-dimensional first-order normal dynamic linear model (NDLM), where Normal and Inverse-Gamma priors are used. The primary efficacy analysis will calculate the Bayesian posterior probability that the dose identified is the most likely ED₉₀ dose that achieves the CSD compared to the placebo arm. At each analysis, three Bayesian probabilities will be summarized for each active dose: the probability of being the ED₉₀ dose, the probability of being statistically superior to placebo, and the probability of being statistically superior to placebo by the CSD. The study will be considered a success in the Bayesian analysis at the completion of 12 months of treatment if there is at least an 80% probability that the ED₉₀ achieves the clinically significant difference from placebo. See [Section 5.4.2](#) for definitions of CSD, ED₉₀, early success and futility.

Censoring

For the clinical efficacy data (i.e. derived ADCOMS, MMSE, CDR-SB, ADAS-cog and FAQ)

- Subjects will be censored at the time of initiation of new AChEIs or memantine treatment regimens if they were not on AChEIs or memantine at randomization, and will be censored at the time of dose adjustment of AChEIs or memantine if they were already on stable treatment with AChEIs or memantine at randomization.

The value of the primary endpoint for censored subjects and censored assessments will be imputed using data up to the censoring time and the Bayesian imputation method.

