5.6.2 Adverse Events

The AE verbatim descriptions (investigator terms from the CRF) will be classified into standardized medical terminology using the Medical Dictionary for Regulatory Activities (MedDRA). Adverse events will be coded to the MedDRA (Version 15.0 or higher) lower level term (LLT) closest to the verbatim term. The linked MedDRA preferred term (PT) and primary system organ class (SOC) will also be captured in the database.

A treatment-emergent AE (TEAE) is defined as an AE that emerged during treatment or within 90 days following the last dose of study drug, having been absent at pretreatment (Baseline) or

- Reemerged during treatment, having been present at pretreatment (Baseline) but stopped before treatment, or
- Worsened in severity during treatment relative to the pretreatment state, when the AE was continuous.

TEAEs and AEs will be followed for the entire duration of the study. Only those AEs that are treatment emergent will be included in summary tables. All AEs, treatment emergent or otherwise, will be presented in subject data listings.

Treatment-emergent AEs (TEAEs) will be summarized by treatment group on the Safety Analysis Set. The incidence of TEAEs will be reported as the number (percentage) of subjects with TEAEs by SOC and PT. A subject will be counted only once within a SOC and PT, even if the subject experienced more than one TEAE within a specific SOC and PT. The number (percentage) of subjects with TEAEs will also be summarized by maximum severity (mild, moderate, or severe). The number (percentage) of subjects with TEAEs will also be summarized by relationship to study drug (possibly related, probably related, and not related). TEAEs of special interest will be summarized similarly.

Adverse events will be summarized by the following subgroups: age (≤ 65 years, $65 < \text{age} < 80$, ≥ 80 years), sex (male, female), race (white, black, Asian, other), region, clinical subgroup (MCI due to AD – intermediate likelihood and mild Alzheimer's disease dementia), presence or absence of ongoing AD treatment (i.e., AChEIs and/or memantine), and *APOE $\epsilon 4$ carrier status* (positive, negative).

The number (percentage) of subjects with TEAEs leading to death will be summarized by MedDRA SOC and PT for each treatment group. A subject data listing of all AEs leading to death will be provided.

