8 DEFINITIONS AND CONVENTIONS FOR DATA HANDLING

The baseline value for efficacy and safety will be defined as the most recent value reported just before first dosing.

- For subjects who start a new AD treatment (AChEIs and/or memantine) and were not on an AD treatment at randomization, a flag will be set to “Yes” at the visit where the AD treatment started and carry forward for all subsequent visits. For subjects who were on an AD treatment at the time of randomization and a dose adjustment to the AD treatment is performed after randomization, a flag will be set to “Yes” at the visit of the dose adjustment and carry forward for all subsequent visits.

The flag should be included in all efficacy data sets. The flag in the efficacy data sets will be used as a censoring mechanism for the primary endpoint described in [Section 5.4.1](#).

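### The definition of concomitant medication leaves out any drug that was both started and stopped during treatment

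*SAP*

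**What the plan says.** Section 5.2.5 sets up two categories and summarises only those two.

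- Prior: "Prior medications are defined as medications that stopped before the first dose of study drug".
- Concomitant, first limb: "started before the first dose of study drug and were continuing at the time of the first dose of study drug". This limb sets no condition on when the drug is later stopped.
- Concomitant, second limb: "started on or after the date of the first dose of study drug and continued up to the last dose".

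The output is also stated: "The number (percentage) of subjects who took prior and concomitant medications will be summarized on the Safety Analysis Set by treatment group", broken down by ATC class and preferred term, with AD and non-AD therapies shown separately.

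Two other sections deal with AD drugs begun on study, and neither refers to the Section 5.2.5 categories. Section 5.4.1 says "Subjects will be censored at the time of initiation of new AChEIs or memantine treatment regimens" if they were on neither drug at randomization, with a parallel rule for dose adjustment in those already treated. Section 8 sets a flag "at the visit where the AD treatment started and carry forward for all subsequent visits", and again treats dose adjustments in the same way.

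**The concern.** A concomitant medication table should show what subjects took while they were being treated. The second limb joins its two conditions with *and*: the drug must start on or after the first dose, and it must also run up to the last dose. A drug begun during treatment and finished before the last infusion fails the second condition. It also cannot be prior, because it did not stop before the first dose. It therefore has no category.

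The omission falls on drugs begun on study, which are the ones that can reflect events during treatment. For AD drugs it also separates the descriptive table from the efficacy rules: a subject can be censored in the primary analysis because of a drug that the AD-therapy table does not count. For non-AD drugs the SAP has no equivalent flag, so the Section 5.2.5 summary is the only place in this document where on-study use would appear.

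**Working it through.** The plan states no figure here and no arithmetic applies. The check is to sort each start and stop pattern under the wording of Section 5.2.5, then compare the result with Sections 5.4.1 and 8.

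**Step 1. Sort the patterns.**

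| Pattern | Prior? | Limb 1? | Limb 2? | Result |
|---|---|---|---|---|
| a. Stopped before first dose | yes | no | no | prior |
| b. Ongoing at first dose, stopped at any later time | no | yes | no | concomitant |
| c. Started on or after first dose, still taken at last dose | no | no | yes | concomitant |
| d. Started on or after first dose, stopped before last dose | no | no | no | unclassified |
| e. Started after last dose | no | no | no | unclassified |

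Pattern d is the defect. Pattern e follows from ending the concomitant period at the last dose, which is an ordinary choice.

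**Step 2. Compare b with d.** A drug ongoing at first dose and stopped on Day 2 is counted under limb 1. A drug started on Day 2 and taken for most of the treatment period, but stopped shortly before the last dose, is not counted. The second has far more overlap with treatment than the first. No purpose of a concomitant medication table explains ranking them this way round.

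**Step 3. Reconcile with the AD-drug rules.** Take a subject on no AD drug at randomization who starts a cholinesterase inhibitor during treatment, stops it two months later, and continues infusions.

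- Section 5.4.1: clinical efficacy data are censored from the start of the drug. The later stop does not undo this.
- Section 8: the flag is set at the start visit and carried to every later visit.
- Section 5.2.5: the drug is pattern d, so the subject is not counted under it in the AD-therapy summary.

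The three sections therefore disagree about the same subject. The mismatch is limited to new starts that later stopped. A subject whose stable AD drug had its dose adjusted was already taking it at first dose, so limb 1 still counts that subject.

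**Step 4. Look for dependence elsewhere.** The dose-response and longitudinal models, the censoring rule, the analysis set definitions in Section 5.2.1 and the success and futility criteria do not use the Section 5.2.5 categories. Only the descriptive summaries are affected.

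**The case against.** The strongest reply is that the drugs that matter for efficacy are handled elsewhere. That is right. Starts and dose adjustments of cholinesterase inhibitors and memantine are censored under Section 5.4.1 and flagged in all efficacy data sets under Section 8. The primary endpoint is rerun without censoring under Section 5.4.1.1, and Section 5.7 allows ad hoc work on such starts. A reader might infer that an imbalance between arms in new symptomatic treatment is hidden. The SAP does not support that: the data to see it are held, whatever the stop date. What remains true is that the SAP commits to no by-arm table of these starts, since Section 8 defines only a flag and Section 5.7 is optional.

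Second, the intended meaning was probably a drug started at any time from first dose up to last dose. That may be so, but the text says otherwise, and a programmer following it would drop the records. Table shells and programming rules are in separate documents (Sections 9 and 11) that are not at hand and might apply a different rule. The finding is therefore about what this SAP states.

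Third, a reader might treat the exclusion of drugs started after the last dose as a further error, because adverse events count as treatment-emergent "within 90 days following the last dose of study drug" and some subjects are followed for efficacy after stopping treatment. It is not an error. Ending the concomitant period at the last dose is common, the adverse event window serves another purpose, and the censoring rule for AD drugs has no last-dose limit.

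**Conclusion.** The point holds as a wording defect with a definite consequence: drugs both started and stopped during treatment are missing from the by-arm medication summaries that the SAP describes, and the AD-therapy summary will not reconcile with the censoring and flag rules. The primary analysis does not change. The correction is worth making because the rule, as stated, produces an incomplete table.

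Two stronger readings should be resisted. A reader might infer that the loss differs between arms, for example because courses given for drug-specific reactions would fall mainly in active arms. The SAP gives no reaction rates and no expected medication use by arm, so this would be conjecture. A reader might also try to put a percentage on the loss by assuming course lengths and random start times. That would give a chance per course under invented durations, whereas Section 5.2.5 counts subjects by drug, and any one qualifying use keeps the subject in the table. The number of subjects affected cannot be stated from this document.

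The conclusion rests on reading the second limb literally and on no separate specification overriding it.

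**What to change.** Replace the two limbs in Section 5.2.5 with one rule: a medication is concomitant if it was taken on at least one day from the date of first dose to the date of last dose, regardless of when it started or stopped. The definition of prior medication can stay as it is.

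Optionally, add a by-arm count of subjects who started a cholinesterase inhibitor or memantine and of those who had a dose adjusted, taken from the Section 8 flag and split by AD treatment status at randomization. Even with the definition corrected, the AD-therapy summary pools drugs ongoing at first dose with drugs begun later, so it would not show new starts on its own.

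The cost is one sentence of SAP text and one changed derivation. The existing definitions already need start and stop timing relative to the first and last dose, so no new data are required. The optional count uses a flag that is already planned.

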5.2.6 Treatment Compliance

Treatment compliance rate is defined as $100\% \times (\text{total number of active infusions subjects actually received}) / (\text{total possible number of active infusions the subjects could receive})$. For example, for a subject assigned to the bi-weekly arms, the total possible number of active infusions the subject could receive will be 26 or 39 over 12 or 18 months of treatment period, respectively; for a subject assigned to the monthly arms, the total possible number of active infusions the subject could receive will be 12 or 18 over 12 or 18 months of treatment period, respectively. Treatment compliance rate will be summarized by treatment group both as a continuous variable and as a categorical variable, with categories <50%, 50% to 75%, 75% to 100%. Subjects in bi-weekly arms with <50% compliance rate and subjects in monthly arms with <75% compliance rate will be excluded from Per Protocol Set.

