Subjects will be from 2 clinical subgroups, collectively designated as EAD for the purposes of this protocol: (a) MCI due to AD – intermediate likelihood and (b) mild Alzheimer's disease dementia. At study entry, subjects will be stratified according to clinical subgroup, *APOE* status (*APOE4* positive and negative), and the presence or absence of ongoing AD treatment with AChEIs or memantine or both. Randomization into the 2 clinical subgroups (see [Inclusion Criteria, Section 9.3.1 of the protocol](#)) is to remain reasonably balanced whereby at least 60% of the total number of subjects will have MCI due to AD – intermediate likelihood clinical subgroup and at least 30% will have mild Alzheimer's disease dementia. The subjects will be randomized into 1 of 6 treatment groups ([Table 1](#)) as explained in [Section 9.4.4](#) and [Section 9.4.5 of the protocol](#). *APOE4* status (positive or negative) must be confirmed for all subjects prior to randomization. After Protocol Amendment 05 based on the request from the Voluntary Harmonisation Procedure (VHP) committee, subjects who are confirmed *APOE4* positive (*APOE4* hetero- or homozygous) will not be randomized to the 10 mg/kg, biweekly dose. Randomization in the Core Study will initially be fixed to each of these dose groups (4:2:2:2:2:2 ratio, placebo to each of the 5 active treatment arms). All study personnel and subjects will be blinded with respect to the dose regimens. After 196 subjects have been randomized into the study, an interim analysis (IA) will be conducted and RAR will guide subsequent randomization into dose groups. Interim analyses and RAR will be repeated after 250 subjects have been randomized and again after each additional 50 subjects until all 800 subjects are randomized, and will then be conducted at 3-month intervals until all subjects complete 12 months of

treatment. A Bayesian analysis will be conducted at 12 months of treatment to assess for early success, and at 18 months of treatment, regardless of whether early success is achieved at 12 months.

Table 1 BAN2401 Dose Regimens

Study Arm	BAN2401 Dose (mg/kg)	Infusion frequency
1	Placebo	Biweekly ^a
2	2.5	Biweekly ^a
3	5.0	Biweekly ^a
4	10.0 ^b	Biweekly ^a
5	5.0	4-week intervals ^c
6	10.0	4-week intervals ^c

a: Biweekly = 2-week intervals

b: Subjects who are confirmed *APOE4* positive (*APOE4* hetero-or homozygous) will not be randomized to the 10 mg/kg, biweekly dose.

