c: Subjects receiving study drug at 4-week intervals will receive placebo at intervening 2-week time points.

An overview of the study design is presented in Figure 1.

[figure not shown]

Figure 1 Design of Study BAN2401-G000-201

R = randomization.

Oversight of the interim analyses and RAR will be conducted by an independent Interim Monitoring Committee (IMC). The IMC will consist of 3 members who are external to the company with expertise in Bayesian adaptive design in clinical trials.

The interim analyses and RAR will be conducted by an unblinded external independent data analysis group in accordance with the protocol. This independent group will provide the interim analysis outcomes to the IMC at each interim look. The IMC will ensure the integrity of the IA and response adaptive randomization process through review of primary efficacy data. In addition, the IMC will act in an independent advisory capacity to monitor the Bayesian IA outcomes according to the early success and futility boundaries pre-specified in the protocol. The IMC will inform the sponsor if the boundaries for early success or futility have been crossed. If the study continues to randomize subjects after statistical futility boundary confirmed by the IMC is crossed, it will be considered a failed study. The IMC will not be charged with any subject safety issues, as this will be the responsibility of an independent DSMB.

A separate unblinded DSMB will be employed at regular intervals to monitor the overall safety of the Core Study and OLE Phase of the study and will make recommendations to the Sponsor as appropriate. In addition, the DSMB will meet when a predetermined number of subjects are randomized to assess whether the option for home infusions is feasible (per DSMB charter, if allowed and conducted according to country and local guidelines; home infusions will not be allowed in Germany). Upon implementation of Protocol Amendment 07, newly enrolled subjects will not be offered the option for home infusions. Subjects opting for home infusions before implementation of Protocol Amendment 07 will be allowed to continue with home infusions for the duration of their participation in the study. Details regarding DSMB membership and operational characteristics will be provided in the DSMB Charter.

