2.0 STATISTICAL MODELING

2.1 Primary Endpoint Modeling

The primary endpoint is the change from baseline to 52 weeks in a composite clinical score. We label the observations of the change from baseline in composite clinical score for subject i , at the 6, 12, 26, 39, and 52 week visits as $Y_{i,6}$, $Y_{i,12}$, $Y_{i,26}$, $Y_{i,39}$, and $Y_{i,52}$, respectively. We model the 52-week primary outcomes as normally distributed,

$$[Y_{i,52}] \sim N(\theta_d, \sigma^2),$$

where d_i is the treatment arm for subject i . The treatment arms are: $d=0$ (control), $d=1$ (3 mg/kg bi-weekly), $d=2$ (5 mg/kg bi-weekly), $d=3$ (10 mg/kg bi-weekly), $d=4$ (5 mg/kg monthly), and $d=5$ (10 mg/kg monthly). □

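### SAP 5.2.6: the compliance denominators for the 4-weekly arms (12 or 18) do not fit the 4-week schedule, and the active-infusion rate cannot be calculated for placebo

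*SAP*

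**What the plan says.** SAP 5.2.6 takes as numerator the "total number of active infusions subjects actually received" and divides by the number of active infusions possible. By way of example it gives denominators for two kinds of arm. The bi-weekly example reads: "the total possible number of active infusions the subject could receive will be 26 or 39 over 12 or 18 months of treatment period". The example for the others reads: "for a subject assigned to the monthly arms, the total possible number of active infusions the subject could receive will be 12 or 18", again for the two periods in turn.

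The rate is reported "with categories <50%, 50% to 75%, 75% to 100" per cent, and it also decides membership of an analysis set: "Subjects in bi-weekly arms with <50% compliance rate and subjects in monthly arms with <75% compliance rate will be excluded from Per Protocol Set". Placebo is not named in the example or in the exclusion rule.

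The schedule is in SAP 3.2, Table 1. Its footnote reads "Biweekly = 2-week intervals", and the table lists placebo at that frequency. The two remaining arms are dosed at 4-week intervals: "Subjects receiving study drug at 4-week intervals will receive placebo at intervening 2-week time points".

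**The concern.** The two example denominators do not describe the same calendar. The bi-weekly figures run on a 52- or 78-week clock. The figures for the 4-weekly arms fit only one infusion per calendar month. If they are programmed as printed, the rate for two of the five active arms can exceed 100%, and the stated Per Protocol cut is not the cut actually applied.

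The placebo gap is separate. SAP 5.4.1.2 compares the ED90 dose with placebo in the Per Protocol Set as well as in the Full Analysis Set, so placebo subjects have to be classified. SAP 5.2.1 defines the Per Protocol Set only as those who complied with the protocol, which leaves 5.2.6 as the SAP's one numeric compliance rule for it. A rule that counts only active infusions gives the control arm nothing to count.

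**Working it through.** **Inputs**
- Bi-weekly denominators 26 and 39; monthly denominators 12 and 18; cuts of 50% and 75% (SAP 5.2.6).
- Infusion intervals of 2 and 4 weeks (SAP 3.2, Table 1).
- Length of 12 months: Appendix 13.2, Section 2.1 says "The primary endpoint is the change from baseline to 52 weeks in a composite clinical score", so 18 months is 52 × 18/12 = 78 weeks.

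**1. Reproduce the plan's figures**
- Bi-weekly: 52/2 = 26 and 78/2 = 39. Both agree with 5.2.6.
- 4-weekly: 52/4 = 13, and 78/4 = 19.5. The latter means 20 infusions if active dosing starts at the first 2-week visit and 19 if it starts at the second. Neither 12 nor 18 is reproduced.
- Only calendar-monthly dosing gives 12 and 18, which is not the Table 1 schedule.

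**2. Score of a fully compliant 4-weekly subject, using the stated denominators**
- 12 months: 13/12 = 108.3%.
- 18 months: 19/18 = 105.6%, or 20/18 = 111.1%.
- All three lie above the top category, which ends at 100%.

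**3. What the 75% cut amounts to**

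| Period | Infusions needed, stated denominator | True share at that number | Infusions needed, 4-week count |
|---|---|---|---|
| 12 months | 0.75 × 12 = 9 | 9/13 = 69.2% | 0.75 × 13 = 9.75, so 10 |
| 18 months, 19 scheduled | 0.75 × 18 = 13.5, so 14 | 14/19 = 73.7% | 0.75 × 19 = 14.25, so 15 |
| 18 months, 20 scheduled | 14 | 14/20 = 70.0% | 0.75 × 20 = 15 |

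In each row the shift is one infusion, in the lenient direction. Section 5.2.6 does not say whether the 12- or the 18-month rate decides membership, so both are shown.

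**4. Placebo**
- Literal reading: 0 active infusions received / 0 possible = 0/0, undefined.
- Placebo treated as a bi-weekly arm, numerator still active infusions: 0/26 or 0/39 = 0%. That is below 50%, so every placebo subject would be excluded.

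**5. The two cut-offs, if the ED90 is a 4-weekly arm and placebo is given the bi-weekly rule**

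This is an illustration only. It assumes the same exponential dropout d by 52 weeks in both arms, exclusion through discontinuation alone, and 18-month denominators. P(excluded) = 1 − (1 − d)^(t/52), where t is the week of the last infusion needed.
- Placebo: 20 of 39 needed, t = 38. 4-weekly with the stated denominator: 14 needed, t = 52.
- d = 20% (the attrition in SAP 4): 15.0% against 20.0%.
- d = 40% (the main case in Appendix 13.2): 31.2% against 40.0%.

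**The case against.** The best defence is that 12 and 18 stand in an example. The general definition is sound: applied to the Table 1 schedule it yields 13, and 19 or 20. SAP 9 also places derivation rules in separate documents. That much stands, and a programmer working from the definition would get the right count. But these are the only denominators the SAP prints, and one copied into code gives the wrong value.

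For placebo, Table 1 lists the arm as bi-weekly. The sensible intention is 26 or 39 infusions with the 50% cut, the word active serving to leave out the intervening placebo infusions of the 4-weekly arms. That is a fair guess at intent, but the text does not say it, and taken literally it excludes the whole arm.

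A reader might go further and infer that the 50% and 75% cut-offs are themselves an error, so that the Per Protocol Set is differentially selected throughout. The SAP does not support this. Different regimens may carry different thresholds, and giving no reason is not a contradiction. At the 18-month cut a retained bi-weekly subject has had at least 20 active infusions, against 14 for a retained 4-weekly subject. If the ED90 is a bi-weekly arm and placebo follows the bi-weekly rule, both sides of the comparison meet the same cut. The asymmetry in step 5 arises only if the ED90 is a 4-weekly arm. That is a real possibility, since SAP 5.4.2 ranks the two 4-weekly regimens first in order of simplicity.

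**Conclusion.** Two defects hold. The 4-weekly denominators contradict both Table 1 and the bi-weekly count in the same section. The effect is full compliance scored at 106% to 111%, and a nominal 75% cut that operates at 69% (12 months) or 70% to 74% (18 months). Only subjects exactly one infusion short of the intended threshold change status. The compliance rate also cannot be computed sensibly for placebo, so the exclusion rule fails for the control arm as written.

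The differing cut-offs are not a defect in themselves. What is missing is a statement of which one applies to placebo when the ED90 is a 4-weekly arm.

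The size rests on 12 and 18 months meaning 52 and 78 weeks, which the 26 and 39 confirm, and on the Table 1 intervals. Whether 19 or 20 applies depends on which 2-week visit starts active dosing, and the SAP does not show this.

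The reach is limited. Apart from the descriptive compliance table, the effect falls on the Per Protocol run of the conventional analysis of the primary endpoint, which is done alongside the Full Analysis Set. The primary Bayesian analysis (SAP 5.4.1) and the secondary analyses (SAP 5.4.4) use the Full Analysis Set, so the primary conclusion is not at risk. The point should be corrected, but nothing turns on it alone.

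**What to change.** 1. Reconcile SAP 5.2.6 with Table 1. Take the 4-weekly denominator from the active infusions scheduled at 4-week intervals: 13 over 12 months, and 19 or 20 over 18 months according to the actual infusion schedule.
2. Define placebo compliance separately, as placebo infusions received over the 26 or 39 scheduled, with a stated Per Protocol cut-off.
3. State which cut-off applies to placebo if the ED90 compared with it is a 4-weekly arm.

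Keep the active-only numerator for the BAN2401 arms. Counting active and matching-placebo infusions together would look simpler, but a 4-weekly subject who missed every active infusion could then still score about 50%.

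The cost is a few lines of SAP wording and one derivation, with no new data. Correcting the 4-weekly denominator should change membership of the Per Protocol Set only slightly. For placebo, membership becomes defined.
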